SD	Standard Deviation
SAE	Serious Adverse Event/Serious Adverse Experience

SOP	Standard Operating Procedure
svPPA	Semantic Variant PPA
tDCS	Transcranial Direct Current Stimulation
US	United States
WAIS-IV	Wechsler Adult Intelligence Scale – 4 th Edition

Protocol Summary

Title	Remotely Supervised Transcranial Direct Current Stimulation (tDCS) for Primary Progressive Aphasia (PPA)
Short Title	RS-tDCS for PPA
Brief Summary	Approximately 30 participants with PPA will be nationally-recruited in an open-label trial of a completely remote intervention to receive four weeks (5 x 30 min daily sessions per week) of active tDCS (2.0 mA, F7: left anodal) paired with simultaneous word naming practice
Objectives	
 - Evaluate the feasibility of RS-tDCS paired with word naming practice in patients with PPA - Collect preliminary efficacy data measured by change in scores on language assessment to support future grant applications
Methodology	Open Label Design
Endpoint	
Primary Endpoints:
 
 - Feasibility judged by study completion percentage. The study will be deemed feasible if participants complete 16/20 RS-tDCS sessions 
Secondary Endpoints:
 
 - language assessment scores (QAB, BNT, COWAT) - The number of trained and untrained language probes identified at treatment end - Self-report questionnaires (ACOM, SAQOL-39, PROMIS Social Roles and Activities, and PROMIS Global Health)
Study Duration	2 years
Participant Duration	Approximately 1 month (4 weeks of intervention)
Duration of IP administration	20x30 minutes daily sessions of IFG tDCS combined with word naming practice
Population	N=30 participants (ages 45-85) diagnosed with early-stage primary progressive aphasia
Study Sites	NYU Langone Health [name]
Number of participants	N=30 participants
Description of Study Procedure	
tDCS is noninvasive brain stimulation device that modulate brain activity delivering a low-intensity electrical current (2.0 mA) through scalp sponge electrodes. The device is preprogrammed to ramp up to 2.0 mA (for 30 seconds), provide constant current throughout session (29 minutes), and then ramp down (for 30 seconds) at the end.
 
Treatment is via telehealth visits, remotely and monitored through live videoconference using the established remotely supervised (RS) tDCS procedure.
 
During the stimulation period, participants will engage in a picture naming exercise during the stimulation as guided by the study tDCS clinicians.

Key Procedures	Active tDCS with simultaneous word naming practice.

Statistical Analysis	
To measure feasibility, individuals will be categorized as “compliant” based on the percentage of study visits completed (16/20). Compliance with the interventions will be assessed by summarizing the distributions of numbers and proportions of completed sessions.
 
Preliminary efficacy will be measured by performance at baseline and study end across study measures (QAB, BNT, COWAT, self-report questionnaires). Change in scores, indicating change following intervention, will be calculated for each compliant participant (defined as above).

----------------------	---

SCHEMATIC OF STUDY DESIGN

Prior to
Enrollment

Confirm eligibility criteria via medical records and self-report;
Obtain informed consent

Baseline
Day 1

Self-report questionnaires (ACOM, SAQOL-39, PROMIS Social Roles and Activities, PROMIS Global Health)
Baseline Language Assessment (Trained and Untrained Words, QAB, BNT, COWAT)
tDCS training and tolerability testing
RS-tDCS + word naming practice

Intervention
Day 2 – Day 19

5 Days a week: **RS-tDCS + word naming practice**

Final Treatment Day
Day 20

RS-tDCS + word naming practice
Post-intervention assessment
Post-stimulation language assessment (Trained and Untrained Words, QAB, BNT, COWAT)
Self-report questionnaires (ACOM, SAQOL-39, PROMIS Social Roles and Activities, PROMIS Global Health)

1 Key Roles

[name], Principal Investigator
NYU Langone Health — Neurology
[name]
[contact]
[contact]

2 Introduction, Background Information and Scientific Rationale

2.1 Background Information and Relevant Literature

The goal of this open-label pilot study is to establish the feasibility of a program of remotely supervised transcranial direct current stimulation (RS-tDCS) paired with word naming practice for people living with the semantic or logopenic variants of primary progressive aphasia (PPA). We will also collect preliminary efficacy data for speech and language outcomes following treatment. These data will be used to inform a grant application to complete the next step of a randomized controlled trial.

Primary Progressive Aphasia (PPA) is a neurological condition associated with a gradual progressive decline in language function, affecting three in 100,000 people annually¹, which is a conservative estimate.

PPA is a devastating language-led neurodegenerative syndrome that is associated with atrophy of predominately left-hemisphere brain regions governing language. The three variants of PPA – semantic, logopenic, and nonfluent/agrammatic – are characterized by distinct neural areas of atrophy including frontal, temporal, and parietal regions^{2,3}. The semantic variant is characterized by word knowledge loss; the logopenic variant by difficulties in word retrieval and repetition that are primarily phonologically mediated, and the nonfluent/agrammatic variant is differentiated by impairment in syntax and motor speech⁴. Beyond the devastating impact that PPA has on language, individuals living with PPA are often middle-aged when diagnosed, which negatively impacts family, work, and overall participation in social roles and activities¹.

Word naming is impaired across all three clinical variants of PPA⁴.

Word-finding difficulties are most pronounced in the early stages of PPA in the semantic and logopenic variants. However, word naming problems are not a salient feature of the nonfluent/agrammatic variant until an advanced stage of disease progression^{5,6}. Targeting word naming training in PPA is of clinical relevance since difficulty finding words is among the chief early complaints². Research suggests that word naming training in PPA can lead to improved language outcomes⁷. However, gains following language training alone remain relatively small⁸. Therefore, researchers have utilized neuromodulation as an adjunctive technique to improve word-naming outcomes.

One such neuromodulatory technique is tDCS, which is a type of noninvasive brain stimulation wherein a mild electrical current is passed through electrodes placed on the scalp. Delivering weak electrical currents (1.0-2.5 mA) via scalp electrodes, tDCS modulates neuronal excitation in the region where applied. tDCS has been extensively studied for a wide range of clinical applications and has a well-established record of safety and tolerability⁹.

tDCS delivered while completing a training activity can reinforce the learning that occurs to improve training outcomes. One established use of tDCS is to pair the stimulation with an ongoing or paired training activity to “boost” the training effect¹⁰⁻¹². In this manner, the use of tDCS has been shown to lead to greater training outcomes from a range of training activities (motor, cognitive, speech and language) by increasing or decreasing the resting potential and/or firing rates¹³. Thus, repeated applications of stimulation facilitate neuroplasticity¹⁴ through mechanisms of LTP of synapses¹⁴⁻²⁰.

tDCS must be dosed in a sustained and cumulative manner for adequate evaluation of its efficacy.

It is clear that tDCS effects are cumulative with adequate evaluation of behavioral effects requiring a period of multiple repeated applications²¹. Preclinical studies have demonstrated that stimulation results in sustained neuronal response²², with increased sensitization following repeated application²¹. This effect is mirrored through consistent findings across clinical studies in that: **1)** a single tDCS session doesn't cause any meaningful behavioral response, and **2)** behavioral changes only follow a sustained period of daily treatment^{23,24}.

[figure not shown]
tDCS is a safe and tolerable treatment that can be delivered to participants at home using the remotely-supervised tDCS protocol²⁵. We developed a remote protocol for use in clinical trials referred to as RS-tDCS, where each daily tDCS session is supervised live via videoconference in order to provide patients with access to the treatment remotely. We have extensive experience in delivering remote tDCS treatment to people living with multiple sclerosis (MS) and an extensive range of other neurological and psychiatric conditions. We also have a clinical tDCS virtual health program where we provide remote tDCS to patients with many different conditions^{26,27}.

When targeted to the inferior frontal gyrus (IFG), tDCS has been shown to improve word naming among individuals with word finding difficulties. The IFG is a key neural circuit for word naming^{28–30}. tDCS has been used in people with aphasia when it is paired with language training. Through both research^{26,31} and our clinical service²⁷, we have initial experience providing RS-tDCS paired with language activities to people living with aphasia. Among individuals with PPA, a recent meta-analysis strongly suggests that language training alongside tDCS exceeds the gains made through language training alone³², with the left IFG as a common neural target across naming studies. Furthermore, we have led the field in determining the feasibility of remotely-supervised tDCS (RS-tDCS) for individuals with PPA with differing typologies and various degrees of severity³¹. However, no study to date has systematically investigated the feasibility and acceptability of RS-tDCS paired with language training in PPA.

In the context of this progressive condition, the treatment goal is to extend the preservation of language functioning through the use of tDCS paired with word naming practice. In this open-label pilot study, we will measure the use of RS-tDCS in people with PPA. It is important for us to first demonstrate the acceptability and feasibility of the treatment. We will also pilot secondary clinical efficacy outcomes, to target personally relevant known words rather than attempting to restore access to forgotten words^{33,34}. Research suggests that recall is higher among those with PPA who have trained words of functional relevance compared to an untrained set of words^{33,35,36}. This study uniquely pairs the evidence from behaviorally-based language training studies in PPA alongside our established RS-tDCS protocol, allowing for determination of the clinical efficacy of tDCS as an adjuvant to PPA treatment.

2.2 Name and Description of the Investigational Device

- **1x1 Mini-CT tDCS device (Soterix Medical Inc.):** The 1x1 Mini-CT tDCS device (see Fig.1, *Panel A*), through the accompanying headset (Fig. 1, *Panel B*) and sponge electrodes (Fig.1, *Panel C*), delivers a weak electrical current (1.0-2.0 mA) to target a specific area of the brain. It is a powered device (9 V) and is easily operated, with a user-friendly large-button keypad interface. The device has specific functions and features that guarantee safety in the remote supervised administration and uniform stimulation dose across sessions and participants. The device allows strict dose control and usage control, employing a one-time use code provided by the study technician to unlock the device for each stimulation session.

2.2.1 Preclinical Data

N/A

2.2.2 Clinical Data to Date

Feasibility of RS-tDCS. We have led the field in remote brain stimulation with the development of the RS-tDCS platform³⁷⁻⁴⁷. In our protocol, participants are provided with remotely-controlled tDCS device, trained in safe and effective operation, and then supervised for daily use through live videoconference⁴⁸ (VSee⁴⁸). Our updated videoconference software for this study will be Zoom. The telehealth connection has resulted in high retention rates across repeated and extended sessions (e.g., >97% completion rates across RCTs to date³⁷⁻⁴⁷). Extensively tested over > 7 years (>9000 remote tDCS sessions in >400 patients to date), it is well validated for use in MS and generalizable for use across most other clinical populations³⁷⁻⁴⁷ (ages 18-85 years, range of neurological and psychiatric conditions, including those with advanced disabilities and/or limited technical experience, and reaching those at socioeconomic disadvantage). Further, the RS-tDCS platform has allowed for continued enrollment of patients with MS in ongoing RCTs during the COVID-19 onsite clinical research pause⁴⁹⁻⁵² (with >100 participants by completing all study procedures remotely).

IFG tDCS regulates language difficulties. IFG tDCS has been established to regulate language difficulties (e.g., in PPA and post-stroke aphasia). In subanalyses of nondepressed MS participants with high baseline negative affect⁵³, 10 or more RS-tDCS sessions, led to reliable negative affect reduction, and the negative affect reduction was maintained at 1-month follow-up. Importantly, these changes have also been linked to increased functional connectivity in Broca's area following treatment⁵⁴.

2.2.3 Dose Rationale

The tDCS protocol of this proposed research will use a stimulation intensity of 2.0 mA that falls well within safety limits established by numerous previous studies applying tDCS with human subjects.

2.3 Rationale

The application of tDCS for language difficulty is not novel on its own³². However, all studies of tDCS in PPA have required onsite delivery of treatment, resulting in small sample sizes and few sessions administered (likely underdosing)^{2,55,56}. Therefore, our main objective is to evaluate the feasibility of reaching PPA participants for study remotely. We will evaluate preliminary efficacy by measuring language output before and after the treatment period.

2.4 Potential Risks & Benefits

2.4.1 Known Potential Risks

Risks of tDCS: The repeated application of tDCS as proposed in this study poses a non-significant risk (NSR) to participants. The safety of this technique has been addressed and tested by multiple researchers who have concluded that tDCS, as applied in a manner similar to our proposed protocol, induces only mild and transient side effects with no report of serious adverse event related to tDCS across clinical trials to date. In >9,000 participant, no undesirable or long-lasting effects have been reported, nor have any subjects reportedly abandoned a study due to discomfort. The most common side effects are warming sensation, itching or tingling sensation under the area of the electrodes. The tDCS protocol of this proposed research will use a stimulation intensity of 2.0 mA that falls well within safety limits established by numerous previous studies applying tDCS with human subjects. In both active and sham tDCS treatment arms, there could be mild discomfort from wearing the headgear.

[figure not shown]
The protocol is designed to have a decision-tree series of checkpoints with "STOP" criteria that must be cleared in order to proceed at each step (see Fig.2).

Risks of RS-tDCS: Extensively verified safety and tolerability of RS-tDCS in the context of research²⁶ and specifically in people with aphasia³¹ based on this experience and well-established safety/tolerability of tDCS in general, we do not anticipate adverse events to be frequent or treatment limiting. No serious adverse events occurred following 6,779 sessions of RS-tDCS²⁶. However, adverse event reporting will occur at each session and risk will be systemically monitored and minimized as outlined in Section 9.7.1. [name] will serve as medical monitor for this study as she has served for all NYU Langone MS Comprehensive Care Center tDCS studies to date. Quarterly meetings will be held with [name] to review adverse events and any adverse event that is judged to be treatment limiting or severe will be immediately addressed by [name] per standard medical care and reported to IRB following guidelines. If a serious adverse event occurs, stimulation will be stopped, participants will be instructed to remove the headset, and to either dial 911 or contact their treating neurologist for follow-up. A

member of the study team will follow up with subjects within the next 1-7 days after such events to document the resolution. This process will be same for both NYU and non-NYU patients. If these cases do occur, treatment will not resume until [name] gives medical clearance to proceed.

Participants will be visually surveyed to rate discomfort on a Likert scale from 1-10 at 3 time points during treatment (session 1, midway, and session 20). If a participant reports a score of 7 or higher for discomfort, the session will be stopped and the study member will consult with the participant for any adjustments needed. Session will start one time again with participant agreement, but will be terminated if a second discomfort score of 7 or higher is reported. Sessions will also be ended if at any point in time if a participant spontaneously reports a discomfort score of 7 or higher. Based on extensive experience²⁶, we have established that this type of discomfort rating will capture any potential type of adverse events as they may occur.

Figure 2. Session safety and tolerability checkpoints and stop criteria

Word naming practice: Word naming practice is not associated with any known risk. To minimize possible frustrating feeling, each session will be monitored in real-time via HIPAA-compliant videoconference with a trained study technician.

Self-report questionnaires: Completing questionnaires about one’s language use may produce some discomfort and/or emotional distress in some patients. Participants will be allowed to take breaks as needed and may skip questions they do not feel comfortable answering so long as the questions do not affect analysis of primary endpoints or eligibility criteria. Individuals with diagnosed psychiatric disorders will be identified by their physician prior to enrollment and would therefore not meet inclusion criteria. While we don’t anticipate this population to have suicidal ideation, the study will follow standard clinical procedures if a subject is suicidal (e.g. refer subject to closest emergency room).

2.4.1.1 Other Risks

Breach of Confidentiality: There is minimal risk of breach of confidentiality. Participants will be assigned a unique study ID and their name will not be used on any of the data collected. All study data survey will be acquired through REDCap and the printed records will be stored in lock cabinet at [name]. Any study data stored

on secure NYU computers and servers will be de-identified. The results of these data collected may be used for publication but will not include the participants' names.

Unforeseeable Risks: While not expected, there may be risks associated with tDCS that are not known at this time.

2.4.2 Known Potential Benefits

Some participants may receive benefit from the word naming practice. There is robust research on the benefits of such interventions among individuals with aphasia.

Based on the literature to date, we anticipate that tDCS combined with word naming practice may improve language functioning among individuals with PPA^{56,57}.

This will be one of the first studies to evaluate a tele-intervention program of tDCS for speech and word naming practice among patients with PPA. The project has the potential to produce an immediately available treatment option for language difficulties among individuals with PPA. This would have immediate and significant clinical utility. In particular, the benefit to the field is the availability of a treatment option for managing symptom burden associated with PPA.

3 Objectives and Purpose

3.1 Primary Objective

To evaluate the feasibility of an RS-tDCS service and concurrent word naming practice.

3.2 Secondary Objectives

Secondary objectives include exploratory analyses to evaluate the potential benefits of tDCS + word naming practice through change scores on language outcomes. This data will inform the power analysis for future study development.

4 Study Design and Endpoints

4.1 Description of Study Design

This study will recruit n=30 PPA patients to receive 20x30 min sessions of active 2.0mA tDCS, combined with simultaneous word naming practice over a 4-week period.

All participants will have a remote consent/research screening visit, baseline visit, 20 tDCS treatment visits, and post-treatment assessment. All visits will be completed remotely using Zoom.

This will be a single site study at NYU Langone Health and will take place over a 2-year period.

4.2 Study Endpoints

4.2.1 Primary Study Endpoints

- Feasibility judged by study completion percentage (16/20 sessions completed per participant)

4.2.2 Exploratory Clinical Endpoints

- Change in language assessment scores (QAB, BNT, COWAT) and self-report questionnaires (ACOM, SAQOL-39, PROMIS Social Roles and Activities, PROMIS Global Health) will be assessed.

5 Study Enrollment and Withdrawal

5.1 Inclusion Criteria

In order to be eligible to participate in this study, an individual must meet all of the following criteria:

1. Ages 45-85 (inclusive)
2. Primary progressive aphasia diagnosis (logopenic or semantic variant)
3. Wide Range Achievement Test (WRAT) score < -1.5 SD, serving as a literacy proxy for premorbid cognitive ability and ensuring English language fluency sufficient for participation in the study procedures. If participants are not fluent enough to perform this task, the Peabody Picture Vocabulary Test (PPVT) will instead be administered with the same cut-off score of < -1.5 SD.
4. WAIS-IV Matrix Reasoning T score < 20 , serving as an index of current general cognitive functioning to exclude those with severe cognitive impairment
5. Stable and continuous access to internet service, email (WiFi "hotspot" to be provided if needed)
6. Fluent in English language (due to outcomes validated in English versions only)

Inclusion criteria may be confirmed through medical records, screening assessments and self-report.

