5.3 Vulnerable Subjects

We will enroll PPA patients early in the disease course and with language loss as their primary impairment. To ensure the ability to meaningfully participate, consistent with all of our RS-tDCS protocols, we will screen to include participants with premorbid intellectual functioning in at least the average range, and screen to exclude those participants with severely impaired current level of cognitive functioning. Consistent with our RS-tDCS protocol, premorbid cognitive impairment will be estimated using the verbal Wide Range Achievement Test-4th edition (WRAT-IV) or the nonverbal Peabody Picture Vocabulary Test-4th edition (PPVT-4) as a proxy of expressive vocabulary, which is an established method to estimate premorbid cognitive ability. A cut off of 1.5 SD below age normative means will be used for exclusion criteria. Current level of cognitive functioning will be estimated using the nonverbal Matrix Reasoning subtest from the Wechsler Adult Intelligence Scale-4th Edition (WAIS-IV) that measures abstract reasoning. A cut-off of 3 SD below age normative means (indicating greater than moderate impairment) will be used for exclusion criteria.

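### The cognitive limits in 5.1 Inclusion Criteria (items 3 and 4) have their inequality signs reversed, so the binding list admits only people whom 5.3 Vulnerable Subjects excludes

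*Combined protocol and SAP*

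**What the plan says.** The lead sentence of 5.1 Inclusion Criteria states that "an individual must meet all of the following criteria". Three limits in that list concern cognition:

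- Item 3, WRAT: "Wide Range Achievement Test (WRAT) score < -1.5 SD, serving as a literacy proxy for premorbid cognitive ability". The item adds that the score should ensure enough English fluency to take part.
- Item 3, PPVT, for people who cannot do the WRAT: it "will instead be administered with the same cut-off score of < -1.5 SD".
- Item 4: "WAIS-IV Matrix Reasoning T score < 20 , serving as an index of current general cognitive functioning to exclude those with severe cognitive impairment".

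5.3 Vulnerable Subjects describes the same screening in prose. On ability before the illness it says: "we will screen to include participants with premorbid intellectual functioning in at least the average range". On present cognition, the stated plan is to "screen to exclude those participants with severely impaired current level of cognitive functioning". For the WRAT or PPVT it says: "A cut off of 1.5 SD below age normative means will be used for exclusion criteria". For Matrix Reasoning it says: "A cut-off of 3 SD below age normative means (indicating greater than moderate impairment) will be used for exclusion criteria".

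5.2 Exclusion Criteria lists no cognitive limit. The Capacity to Consent text, under Consent Procedures and Documentation, names the WRAT/PPVT and Matrix Reasoning together and gives a single limit of 3.0 SD below the age norm, which it describes as a limit for inclusion.

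**The concern.** A less-than sign in a list where every item must be true selects people below the limit. Item 4 thus contradicts itself within one sentence: it requires a score in the severely impaired range in order to keep severe impairment out. Item 3 fits its purpose no better, since requiring a low literacy or vocabulary score does not ensure fluency.

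These criteria decide who enters the study and to whom the primary feasibility result (4.2.1 Primary Study Endpoints) applies. Staff who follow 5.3 will enrol people who fail 5.1. Under 14.3 Protocol Deviations any noncompliance with the protocol is a deviation and is reported to the IRB, so each such enrolment would count as one. Staff who follow 5.1 alone would seek out the impairment that item 4 is meant to exclude. The study is also meant to inform a later randomised trial (2.1), so the error could be carried into that protocol.

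**Working it through.** **1. Direction, section against section**

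| Measure | 5.1 Inclusion Criteria, as written | 5.3 Vulnerable Subjects | Capacity to Consent |
|---|---|---|---|
| WRAT or PPVT | Include if below -1.5 SD | Exclude on a limit of 1.5 SD below the mean | One limit, 3.0 SD below the norm |
| Matrix Reasoning | Include if T is below 20 | Exclude on a limit of 3 SD below the mean | Same 3.0 SD limit |

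**2. Size of the limits.** On the usual T scale (mean 50, SD 10; an assumption, as the protocol does not define it), T = 20 gives z = (20 - 50)/10 = -3.0. The Matrix Reasoning limit therefore has the same size in all three places. The WRAT/PPVT limit has the same size in 5.1 and 5.3. Between those two sections only the direction differs.

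**3. Share of a normative population on each side.** The documents give no score distribution for PPA, so standard normal scores are used purely as an illustration.

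- Below -1.5 SD: P(Z < -1.5) = 0.06681, or 6.7%.
- Below T = 20: P(Z < -3) = 0.00135, or 0.135%.
- Below both, the only group 5.1 admits: with independent scores, 0.06681 × 0.00135 = 0.0000902, or 0.009%. With a bivariate normal correlation of 0.5 the share is 0.00076, and at 0.7 it is 0.00116. The upper bound, with the lower group fully nested in the other, is 0.00135, or 0.135%.
- Above both, the group 5.3 intends: 1 - 0.06681 - 0.00135 + P(below both). This is 0.9319 if independent and 0.9332 if nested, or 93.2% to 93.3%.

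Nobody can be below both limits and above both limits, so the two groups are disjoint whatever the distribution.

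**4. What remains after the signs are turned (WRAT/PPVT only)**

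- *1.5 SD against 3.0 SD.* If the capacity text replaces the limit in 5.1 and 5.3, eligibility changes for scores from -3.0 to -1.5 SD: 0.06681 - 0.00135 = 0.06546, about 6.5%. If it is only an additional floor, nobody's eligibility changes. The protocol does not say which applies.
- *Average range against 1.5 SD, within 5.3.* The average range is not defined. If it begins at -1.0 SD, the gap to the limit holds 0.1587 - 0.0668, about 9.2%. If it begins at -0.67 SD, the gap holds 0.2514 - 0.0668 = 0.1846, about 18.5%.

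**The case against.** The strongest reply is that this is an evident slip. Section 5.3 states the intent plainly, supplies exclusion limits in prose, and would turn away the very people the literal signs admit. The capacity assessment adds a further check before enrolment. Read as a whole, the protocol does not open the door to severe impairment. This is fair, and it narrows the harm: the result is a contradiction between a binding list and the text that explains it. It does not make the list correct, because people who satisfy 5.3 still fail 5.1.

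A second reply is that a symbol was misread when the PDF was converted. That cannot be ruled out from the text alone, and the stray space after the 20 in item 4 hints at conversion trouble. However, the less-than sign appears three times across items 3 and 4, and the same character reads sensibly in 5.2 Exclusion Criteria (seizure within 5 years). The sponsor can settle this by looking at the source file.

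Third, the percentages describe no PPA population. That is true, but the contradiction does not depend on them.

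Fourth, the mention of an average range may be loose prose that the 1.5 SD figure is meant to make exact, and the 3.0 SD sentence may belong only to the capacity assessment. Both readings are possible, so these remain secondary points that need clarifying.

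**Conclusion.** The point holds. Items 3 and 4 are wrong as written: their direction is opposite to item 4's own purpose and to 5.3, and no other section corrects them. All 30 planned participants, if enrolled as 5.3 intends, would fail 5.1. The normative shares in the working show how completely the two readings diverge; they rest on normal scores, a T scale with mean 50 and SD 10, and a correlation varied over its range because none is given. The direction conflict needs none of these assumptions. The fault must be fixed even though the intent is recoverable, because it sits in the operative eligibility list. The unsettled WRAT/PPVT limit is a lesser fault whose effect depends on how the capacity text is meant.

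**What to change.** - In 5.1 Inclusion Criteria, turn the inequalities in item 3 (WRAT and PPVT) and item 4 (Matrix Reasoning) so that they agree with item 4's stated purpose and with 5.3. State how a score exactly at a limit is treated.
- Reconcile 5.1, 5.3 and the Capacity to Consent text so that one WRAT/PPVT limit applies throughout, and either define the average range in 5.3 or remove it. Which value applies is for the sponsor to decide.
- Say whether the 3.0 SD sentence is an eligibility rule or only part of the capacity assessment, and state its direction clearly.

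This is a wording amendment that needs IRB approval before it takes effect (13.2 Institutional Review Board). It adds no tests and no participants.
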